The general approach for an IPTW analysis involves calculating the inverse probability weights and then using these weights to estimate the treatment effect. As the first step, the estimated probability of treatment assignment will be obtained from a logistic regression model where the treatment assignment (treatment vs. control) will be regressed on a set of covariates or confounders. The treatment weights derived from the PS might exhibit instability due to the fact that patients receiving palbociclib + AI treatment could have PS closer to 0, while patients receiving AI monotherapy might have scores closer to 1. Consequently, extreme weights and inflated variance can occur. To mitigate this potential problem, we will calculate stabilized IPTW (sIPTW), as suggested by [Pezzi et al. \(2016\)](#), [Xu et al. \(2010\)](#), and [Shiba and Kawahara \(2021\)](#). By employing sIPTW, the point estimates of the treatment effect will remain unaffected, but it can lead to a more accurate estimation of the variance. Once the stabilized inverse probability weights are calculated for each individual, they will be used to estimate the average treatment effect by comparing the weighted outcomes between the treatment (palbociclib + AI) and control (AI alone) groups.

In the PSM technique, each subject in the palbociclib + AI cohort will be matched to a subject in the AI alone cohort using a 1-to-1 matching with no replacement, using the nearest neighbor matching algorithm with potential use of a caliper (no larger than 0.1 standard deviation).

PFIZER CONFIDENTIAL

Covariate balance will be examined before any adjustment for the PS and after adjusting for the PS (using both sIPTW and PSM techniques). If no significant differences are observed among all baseline measures between the treatment groups, the treatment effect that is calculated from the 2 methods based on the weighted and matched population can be considered to be the true effect. Subsequently, depending on the quality of balance, the endpoint (OS) may be assessed using one or both techniques, in addition to the multivariable CPH regression analysis (Austin, 2014; Buchanan et al., 2014).

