## 9.9 Strengths and Limitations of Research Methods

This study is based on the analysis of the SEER-Medicare database—a database with a diverse array of demographic and clinical information on patients with incident diagnosis of cancer in the Medicare population in the US who are generally 65 years or older. The linkage of Medicare claims data with SEER registry data provides confirmatory data on cancer diagnoses along with precise dates, which in turn make it possible to attribute treatments as specific lines of therapy in alignment with their approved indications and guideline recommendations; this substantially minimizes the risk of misclassification—an inherent limitation in many other commonly used population-based administrative claims data sources in the US. The availability of up-to-date validated vital statistics data, as described in Section 9.4, further makes the database a unique and authoritative data resource for evaluation of survival outcomes in older patients with cancer, especially those represented in the US Medicare population.

There are certain limitations that are typically inherent in studies based on secondary data sources and are applicable to this current study as well:

PFIZER CONFIDENTIAL

- Patients are not randomized to treatment and control groups, and as such, the lack of random assignment may lead to selection bias. We plan to adjust for differences in baseline characteristics and risk factors that are observable in the database, but imbalances in many unobserved characteristics (e.g., performance status, laboratory test results, genetic mutations) may introduce unmeasured confounding.
- The US-labelled indication for palbociclib includes patients who were initially diagnosed at an earlier stage but later progressed to have advanced or metastatic disease; however, this analysis will be restricted to patients with de novo metastatic disease given limitation of the data source. This could potentially limit the generalizability of study findings beyond patients who are not diagnosed at the metastatic stage, but would be an appropriate approach in consideration of the fact that SEER does not collect information about progression or recurrences, and proxy methods to identify recurrences in the SEER-Medicare database are shown to have low sensitivity and specificity, especially among older patients (Hassett et al., 2014; Warren et al., 2016).

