7.2 STATISTICAL ANALYSES

7.3 ANALYSES FOR PRIMARY OBJECTIVE

For the primary objective, the association between primary independent variable (treatment type: palbociclib + AI or AI alone) and the outcome variable (OS) will be assessed using unadjusted Kaplan-Meier analysis and multivariable methods. The primary method of analysis to account for observed confounders will be stabilized inverse probability of treatment weighting (sIPTW). Additionally, as sensitivity analyses, multivariable Cox proportional hazards (CPH) regression and propensity score matching (PSM) will be performed. *Both IPTW and PSM are propensity score (PS)-based methods commonly used to achieve balance between treatment and control groups in retrospective cohort study designs.* All methods are described below in detail.

Kaplan-Meier Analysis

Time-to-event outcome (i.e., OS) will be described using unadjusted Kaplan-Meier analyses; median time-to-event (in months) and landmark probabilities of event at various timepoints (e.g., 12 months, 24 months) will be estimated, along with 95% CIs and log-rank *P* values. Graphical displays of the data will also be generated as appropriate. Kaplan-Meier analysis may also be performed using the stabilized weights or among the PS-matched groups (see details in this section below), and the weighted or PS-matched survival curves may be drawn.

Cox Proportional Hazards Regression

The CPH regression model may be used to estimate a hazard ratio of the OS, along with 95% CI, for the primary exposure—a dichotomous variable indicating whether the patient received AI + palbociclib versus AI alone—and for each of the control variables included in the model, indicating higher or lower rate of death (relative to a reference category) at any given point in time after the index date. The patient demographic and clinical characteristics that will be considered for confounding adjustment in the model are described earlier in [Table 5-2](#).

Propensity Score Estimation

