As the first step in implementation of PS-based methods (IPTW and PSM), the PS (i.e., the estimated probability of treatment assignment) will be obtained from a logistic regression model where the treatment assignment (treatment vs. control) will be regressed on a set of covariates or confounders. The baseline covariates or control variables that will be considered for adjustment in the multivariable logistic regression for deriving treatment probabilities (i.e., PSs for IPTW and PSM) are described earlier in [Table 5-2](#). The following variables will be included in the model: age group, race, year of mBC diagnosis, marital status, geographic status of residence, median household income, LIS coverage, tumor grade at initial diagnosis, involvement of metastatic sites at initial diagnosis (bone, brain, liver, and lung as independent binary variables), and NCICI score category. If any covariates are identified to have missing data, they may be coded as “missing” or “unknown” and included as categorical variables in the model.

Covariate Balancing

The following process will be implemented to determine whether there is sufficient overlap between the patient populations of the 2 treatment cohorts:

- Compute the standardized mean difference in PS for each level of each baseline covariate
- Graphically assess differences in the full distribution of each covariate between 2 treatment cohorts
- An absolute standardized mean difference < 0.1 indicates negligible difference and is considered a good balance

Covariate balance will be examined using both IPTW and PSM techniques as described below. Subsequently, depending on the quality of balance, the endpoint (OS) may be assessed using one or both techniques (Austin, 2014; Buchanan et al., 2014).

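### SAP 7.3 applies its balance criterion to the propensity score within covariate levels, so a covariate outside the PS model can pass while still imbalanced

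*SAP*

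**What the plan says.** Under Covariate Balancing, SAP 7.3 lists three bullets, introduced as a process "to determine whether there is sufficient overlap between the patient populations of the 2 treatment cohorts".

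- The first defines the statistic: "Compute the standardized mean difference in PS for each level of each baseline covariate".
- The second is visual: "Graphically assess differences in the full distribution of each covariate between 2 treatment cohorts".
- The third gives the threshold: "An absolute standardized mean difference < 0.1 indicates negligible difference and is considered a good balance". It does not restate the variable whose SMD is meant. The only SMD defined is that of the PS.

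Two decisions depend on the outcome. The same part of SAP 7.3 says that "depending on the quality of balance, the endpoint (OS) may be assessed using one or both techniques". Its IPTW paragraph allows further adjustment, in the weighted Cox model, for covariates that remain imbalanced.

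SAP Table 5-2 lists Medicaid dual eligibility as a covariate but marks it as not for use in the PS model. Hispanic origin is also in Table 5-2 and is not among the variables that SAP 7.3 lists for the model, which includes race. Age and NCICI score enter as categories, although Table 5-2 also defines them as continuous.

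Protocol 9.7.1 says that covariate balance is examined before and after PS adjustment, and speaks of differences in baseline measures.

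**The concern.** A balance check should compare the distribution of each covariate between the cohorts. The statistic as written fixes the covariate at one level and compares the PS. The covariate does not vary within its own level, so the result carries no direct information on whether that level is equally common in the two cohorts.

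The gap matters most after weighting. The weights are functions of the fitted PS, so a reasonably fitted model brings the weighted PS distributions together. A covariate that never entered the model can stay imbalanced unseen. It would then not be selected for residual adjustment, and the weighted cohorts would be reported as balanced in a non-randomized comparison whose stated aim (SAP 3) is to show superiority.

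**Working it through.** The plan gives no figure to reproduce: 0.1 is a criterion, and no sample size or event count is stated. All prevalences and coefficients below are assumptions. The question is only whether the two statistics can disagree, and by how much.

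**Formulas**

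- Covariate SMD (binary): (p1 − p0) / √{[p1(1 − p1) + p0(1 − p0)]/2}.
- Statistic as written, within level x: (mean PS in cohort 1 − mean PS in cohort 0, among patients at level x) / √[(s1² + s0²)/2], with s1 and s0 the PS standard deviations at that level.
- Stabilized weight: P(treated)/PS for treated patients, P(control)/(1 − PS) for controls.

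**Step 1: one covariate, 70% v 30%.** The covariate SMD is 0.40/√[(0.21 + 0.21)/2] = 0.40/0.458 = 0.87. The PS depends on this covariate alone, so it is constant within each level and the PS difference is 0.

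**Step 2: before weighting** (200,000 simulated patients, fitted main-effects logistic PS).

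- One dominant covariate with SMD 0.81: the PS SMD within its own levels is 0.013 and 0.015. Within levels of the other covariates, whose own SMDs are at most 0.008, it is about 0.81. The cohort fails, but the check points at the wrong covariates.
- Twelve covariates, largest SMD 0.42: within-level PS SMDs run from 0.47 to 0.65, so the cohort fails. A covariate unrelated to treatment (SMD 0.005) shows PS SMDs of 0.64 and 0.65 in its two levels.

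**Step 3: after stabilized weighting, PS model correct** (the same twelve covariates). Modelled covariate SMDs are at most 0.001 and PS SMDs at most 0.017. Both checks pass, as they should.

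**Step 4: after stabilized weighting, one covariate left out of the PS model.**

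| Simulation | SMD of omitted covariate | Largest within-level PS SMD |
|---|---|---|
| 200,000 patients; four modelled covariates (log odds ratios 0.9, 0.6, −0.5, 0.4), omitted covariate 1.0 | 0.39 | 0.024 |
| 300,000 patients; age-band PS model | −0.21 | 0.009 |
| As above, steeper age gradient | −0.20 | 0.020 |
| Separate check, other assumed coefficients | about −0.30 | 0.032 |

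The written rule passes each row at 0.1; the covariate SMD fails each row. For scale, 20% v 10% is 0.10/√[(0.16 + 0.09)/2] = 0.28, and 30% v 10% is 0.20/√[(0.21 + 0.09)/2] = 0.52.

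**Step 5: after stabilized weighting, an interaction left out of the PS model.** Marginal covariate SMDs are at most 0.004, yet within-level PS SMDs reach 0.69, and the product of the two interacting covariates has SMD 0.37. A second check with other coefficients gave PS SMDs up to 0.31 with modelled covariate SMDs near 0. Here the PS statistic detects something that marginal covariate SMDs miss.

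A numerical search also found cohorts in which modelled covariates are imbalanced and every within-level PS SMD is below 0.1. They need special within-arm correlations, so I give them no weight.

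**The case against.** **A drafting slip.** The heading, the level-by-level wording, the usual 0.1 threshold and Protocol 9.7.1 all suggest that covariate SMDs were meant. This is probably right, but the SAP is what a programmer will follow, so it supports correcting the text.

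**The second bullet compares covariates directly.** It does, and baseline characteristics are also tabulated. However, the graphical comparison has no pass/fail rule and does not say whether it is weighted, so it does not replace the numeric criterion.

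**Stronger readings.** A reader might infer four things that the documents or the calculations do not support.

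- *That the check is bound to pass after weighting.* Step 5 shows that it can fail, and usefully. Step 2 shows that ordinary unweighted imbalance fails it too.
- *That coarse age bands prove the point.* In a simulation with a banded-age PS, age within the ≥80 band had a weighted SMD of −0.37, but age overall only −0.066. A covariate SMD on continuous age would also pass at 0.1, so this example does not separate the two checks. Any bias from banding is a matter of the PS model, not of the diagnostic.
- *That the primary method is left open.* SAP 7.3 names stabilized weighting as primary, and SAP 7.3 and 7.6 commit to matching and multivariable Cox regression as sensitivity analyses. The sentence on one or both techniques is loose wording against an explicit choice.
- *That passing balance would establish causality.* Protocol 9.7.1 says the effect from "the weighted and matched population can be considered to be the true effect", but Protocol 9.9 concedes that unobserved differences "may introduce unmeasured confounding". The sentence is not carried into the SAP and changes no analysis.

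**Conclusion.** The concern holds as a specification defect. The only numeric balance rule in the SAP is defined on the wrong variable. Followed literally, it can pass a covariate whose absolute SMD is about 0.2 to 0.4, two to four times the SAP's own threshold, while every within-level PS SMD is about 0.03 or less.

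That size rests on assumed coefficients and on an omitted covariate related to treatment. A covariate correlated with modelled ones would be partly balanced through them, as dual eligibility may be through low-income subsidy coverage, and its residual imbalance would be smaller. The documents give no data to settle this. Nothing here shows that the actual cohorts will be imbalanced or the hazard ratio biased. The correction should be made because the check informs residual adjustment in the primary analysis and the use of the PS techniques.

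**What to change.** In SAP 7.3, Covariate Balancing, replace the first bullet with wording such as:

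> For each baseline covariate in Table 5-2 (every level, plus continuous age and continuous NCICI score, and including covariates not in the PS model such as dual eligibility), calculate the SMD between cohorts unweighted, after sIPTW and in the matched set. Apply the |SMD| < 0.1 criterion to these values. Show the PS distributions by cohort separately, as an overlap check.

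The within-level PS comparison may stay as a supplementary check of PS specification and overlap, without the role of balance criterion. State that the covariate SMDs after weighting decide which covariates receive residual adjustment in the weighted Cox model. Align the sentence on one or both techniques with the opening of SAP 7.3, so that sIPTW stays primary and PSM stays a sensitivity analysis whatever the balance result.

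The cost is a few sentences of SAP text. Covariate SMDs are standard output and need no new data.

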For the assessment of OS, Kaplan-Meier analysis may also be performed using the stabilized weights or among the PS matched groups, and the weighted or PS-matched survival curves may be drawn. Subsequently, Cox regression analysis may be performed using the stabilized weights or among the PS-matched groups. Point estimate (i.e., hazard ratio) will be derived, as applicable, along with 95% CI and *P* value using robust variance estimation. Any covariates with residual imbalance may be adjusted for in this step.

All patients will be followed from the start of therapy line through death or the end of available study follow-up, whichever is earliest. Section 9.7.3 discusses potential sensitivity analyses; e.g., adjusting for subsequent treatments received.

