IPTW: The general approach for an IPTW analysis involves calculating the inverse probability weights and then using these weights to estimate the treatment effect. The IPTW for each patient is the inverse of their PS for their respective treatment group. For exposed individuals, the weight is $1/PS$, and for unexposed individuals, it is $1/(1 - PS)$. The treatment weights derived from the PSs might be large because patients receiving palbociclib + AI treatment may have PSs closer to 0, while patients receiving AI monotherapy may have scores closer to 1. Consequently, extreme weights and inflated variance can occur. To mitigate this potential problem, we will calculate sIPTW, as suggested by Pezzi et al. (2016), Xu et al. (2010), and Shiba and Kawahara (2021). By employing sIPTW, the point estimates of the treatment effect will remain unaffected compared with unstabilized weights while leading to a more accurate estimation of the variance. Once the stabilized inverse probability weights are calculated for each individual, they will be used to estimate the average treatment effect by comparing the weighted outcomes between the treatment (palbociclib + AI) and control (AI alone) groups. For Kaplan-Meier analysis, sIPTW will be applied to assess weighted median OS and 95% CI; weighted survival curves will be drawn and weighted landmark probabilities of event at various timepoints will be estimated (e.g., 12 months and 24 months). For assessing weighted estimate of hazard ratio for the treatment type (AI + palbociclib vs. AI alone), sIPTW will be applied to the Cox proportional hazards model. Variance will be estimated using robust variance estimation method to account for the weighted nature of the data. Point estimate (i.e., hazard ratio) will be derived along with 95% CI; any covariates with residual imbalance may be adjusted for in this step.

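### The primary sIPTW hazard ratio takes its 95% CI from a robust variance that ignores estimation of the propensity score, so the interval can be miscalibrated in either direction; the weighted Kaplan-Meier intervals have no stated method.

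*SAP*

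**What the plan says.** SAP 7.3 names sIPTW as the primary method. Under Propensity Score Estimation, "the PS (i.e., the estimated probability of treatment assignment) will be obtained from a logistic regression model", with a listed set of covariates ("The following variables will be included in the model: age group, race, year of mBC diagnosis, marital status", and others). For the hazard ratio, "sIPTW will be applied to the Cox proportional hazards model", and the next sentence gives the only variance instruction: "Variance will be estimated using robust variance estimation method to account for the weighted nature of the data". Protocol 9.7.1 likewise plans the hazard ratio "along with 95% CI and *P* value using robust variance estimation". Neither document mentions a bootstrap or any variance that allows for the PS having been estimated.

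The same SAP paragraph warns about the raw weights: "Consequently, extreme weights and inflated variance can occur". Stabilization is the only stated remedy; there is no truncation rule.

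For the weighted Kaplan-Meier analysis, "sIPTW will be applied to assess weighted median OS and 95% CI", together with weighted landmark probabilities (12 and 24 months as examples). No variance or interval method is named for either. The robust-variance sentence stands between the Cox sentence and the hazard-ratio sentence, so it reads as applying to the Cox model only. No interval is stated for the weighted landmarks; the landmark intervals earlier in SAP 7.3 belong to the unadjusted analysis.

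**The concern.** The usual robust (sandwich) variance takes each weight as a fixed constant. Here the weights are functions of coefficients estimated from the study patients. Fitting the PS removes part of the chance imbalance in the covariates. If those covariates predict death, the weighted log hazard ratio then varies less from sample to sample than the sandwich reports. The listed covariates include age, metastatic sites, grade and comorbidity, which can be expected to be prognostic. When a few weights are very large, the sandwich can err the other way, because it understates spread in finite samples.

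At stake is the calibration of the interval on which the study's superiority aim (SAP section 3) will be judged. Protocol 9.5 says the database fixes the cohort size, so lost precision cannot be recovered by adding patients. For the weighted median the risk is different: a default method chosen at the programming stage may ignore what weighting does to the variance.

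**Working it through.** **Nothing to reproduce.** Protocol 9.5 reports no sample size estimation, and the documents give no event count, allocation, alpha or power. Every simulation setting below is therefore an assumption.

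**Size of the PS model.** SAP 7.3 lists 13 covariates, counting the four metastatic sites separately. With race, marital status and region in their collapsed forms from SAP Table 5-2, the coefficients number age 3 + race 1 + year 4 + marital 3 + region 2 + income 4 + LIS 1 + grade 3 + sites 4 + NCICI 2 = 27.

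**Robust SE against the true SD of the weighted log hazard ratio.** A ratio above 1 means the interval is too wide.

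| Simulation (assumed settings) | Robust SE / true SD | Coverage of 95% CI |
|---|---|---|
| A: N = 1,500, about 815 deaths | 0.077/0.071 = 1.08 to 0.084/0.076 = 1.11 | 96.5-97.1% |
| B: moderate selection, prognostic covariates (largest weight about 4) | 1.05-1.10 | 96.3-97.1% |
| B: moderate selection, non-prognostic covariates | 0.98-1.00 | 94.8-95.3% |
| B: intermediate selection (largest weight 8-11) | 1.00-1.03 | 95.2-96.1% |
| B: strong selection (largest weight 12-20) | 0.89-0.99 | 92.6-95.5% |
| C: 13 covariates, HR 0.76 | 1.06-1.15 | 96-98% |

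Simulation B used the 27-coefficient PS, HR 0.76 (the value cited in both documents for palbociclib + AI versus AI alone), 40% treated, N = 500, 1,000 and 2,000 (about 205, 410 and 820 deaths) and 2,000 replicates per scenario. In the setting of A, the excess width fell to about 4% at N = 2,500.

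**Two candidate repairs.**
- Large-sample correction (B): removing from the SE the part explained by the PS scores gave 0.78-1.00 of the true SD. At N = 500 its coverage was 88.4-94.3%.
- Bootstrap that refits the PS (C): 0.96-1.09 of the true SD, coverage 94-96%. With 300 cohorts per scenario, the Monte Carlo error of a coverage near 95% is about √(0.95 × 0.05/300) = 1.3 points. C contains no scenario in which the robust SE was too small.

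**Power, conditional on assumed values.** If the reported SE differs from the true SD, power at two-sided 0.05 is Φ((−ln HR − 1.96·SE)/SD). At HR 0.80, −ln HR = 0.2231. Taking the SEs and SDs of A and pairing the ends of their ranges (an assumption):
- Milder confounding, SD 0.071. Robust: (0.2231 − 1.96 × 0.077)/0.071 = 1.02, power 84.5%. PS-corrected SE 0.0726: 1.14, power 87.3%.
- Steeper confounding, SD 0.076. Robust: (0.2231 − 1.96 × 0.084)/0.076 = 0.77, power 77.9%. PS-corrected SE 0.0741: 1.02, power 84.7%.

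The loss is about 3 to 7 points. At HR 0.76 the same sums give about 1 to 3 points. Entering the robust SE as both the reported SE and the estimator's spread would overstate the loss.

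**Weighted Kaplan-Meier (B, treated arm, 24 months).** Greenwood with weights read as case counts gave 0.52-0.91 of the true SD. By 2Φ(1.96·r) − 1, a nominal 95% interval would then cover about 69% (r = 0.52) to 93% (r = 0.91). A robust SE with weights taken as known gave 0.79-1.02.

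**The case against.** Robust variance is a recognised choice for weighted Cox models, and here it is pre-specified. Where it errs towards width, coverage is at least nominal and the false-positive rate is below nominal, so a superiority claim is not endangered. On that view, asking for a more efficient variance is preference rather than correction. This stands for the moderate-weight case, but not where selection is strong: coverage fell as low as 92.6%, and the SAP itself foresees extreme weights.

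A reader might infer that the primary interval is certain to be too wide and that power is lost. The documents do not support this. The direction depends on how prognostic the covariates are and how extreme the weights become; with non-prognostic covariates the error vanishes, and with strong selection it reverses. No loss of power can be computed from documents that state neither size nor events.

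A reader might also infer that the weighted Kaplan-Meier intervals suffer the same fault. They do not: there the method is unnamed, and the likely default error makes the interval too narrow. Nor does the SAP promise intervals for the weighted landmarks.

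Finally, a variance from stacked estimating equations looks like an equal remedy. As a large-sample correction it is not a safe default, because such a correction was too small in the smaller simulated cohorts and the real cohort size is unknown.

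**Conclusion.** The concern holds as a matter of calibration and incomplete specification. The primary hazard ratio's interval comes from a variance that ignores estimation of the PS. With prognostic covariates and moderate weights, the SE is about 5-15% too large and coverage about 96-98%; with extreme weights it can be too small, by up to 11% in the assumed scenarios. Which case applies cannot be known before the weights are seen. The 3-7 point power loss at HR 0.80 is illustrative and rests on assumed SEs, SDs and their pairing.

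The missing method for the weighted median is a separate gap and a clear one: the SAP would permit an interval that is materially too narrow. All magnitudes depend on assumed cohort size, events, allocation, selection and prognostic strength.

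**What to change.** In SAP 7.3:
1. Take the primary hazard ratio's 95% CI and P value from a patient-level bootstrap of 1,000 or more resamples. Refit the PS, the stabilized weights and the Cox model in each resample, including any covariates added for residual imbalance. State the interval type (percentile, or normal with bootstrap SE), the seed, and the handling of resamples in which the PS model fails to converge.
2. Report the robust SE alongside as a check, and say that the bootstrap interval governs. Do not make the large-sample stacked variance the default.
3. Use the same resamples for the 95% CI of the weighted median OS and for any interval given with the weighted 12- and 24-month probabilities. State what is done when a resampled curve does not reach its median.
4. Align the variance sentence in Protocol 9.7.1.

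The cost is computing time and a short SAS macro, with no change to the data. Settling it before analysis avoids a choice of variance made after the results are seen. The bootstrap check above did not cover extreme weights, so the weight distribution should be reported with the result.
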